This feasibility trial is being performed in collaboration with the BAApres Training and Intervention Fidelity study (IRB00084011). Under this grant, individual study teams conduct non-randomized feasibility trials to assess intervention feasibility and provide initial parameter estimates on specified outcomes.

The AA interventionists for this study will complete Auricular Acupressure training modules and complete competency assessments and intervention assessments throughout the study. Study teams will include the possibility that a study participant may be part of a competency assessment and that their session may be recorded and securely uploaded to a server per IRB and Institutional policies.

Objectives:

The purpose of this study is to determine if the addition of auricular acupressure to the typical pharmacological regimen given to patients on the chronic pain/addiction service will lower pain scores and decrease pain medication usage.

Setting:

This will be a study utilizing the location of Atrium Health Wake Forest Baptist (Main Campus) for initiation of study procedures.

Subject selection criteria

Any patient admitted to Atrium Health Wake Forest Baptist for which our chronic pain/addiction medicine service is consulted.

Inclusion:

Patient admitted to the hospital with a chronic pain/addiction medicine service consult.

1. Age > or equal to 18
2. History of documented chronic pain with or without opioid use disorder
 - a. Polysubstance abuse or opioid use disorder
 - b. **Or opioid use (documented as home medication)**
3. Expected length of stay (admission) is at least 5 days at the time of recruitment
4. Able to read and understand the informed consent form

Exclusion:

1. Patient refusal
2. Patients who are at a risk of leaving against medical advice (AMA) during their current admission may be excluded per the investigator's discretion
3. Since this is a feasibility pilot, only English-speaking participants will be eligible.
4. Inability to communicate via telephone
5. Participants with a history of skin disease (e.g., psoriasis) involving the ear, adhesive allergy, recent scar tissue on ear, or current abrasions or cuts on ear,
6. Cognitive impairment (delirium, dementia)
7. Physical impairment preventing them from applying pressure to the beads
8. Patients with cardiac pacemakers (contraindication to POINTER PAL)

9. Use of some types of hearing aids (obstructing the placement of beads)

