Opioid use - Pre-Admission Opioid requirement and change from baseline (medication used during the intervention and as reported afterwards vs. home dose before the study started) collecting type, frequency and milligram use and date and time of last use prior to admission measuring mean/median changes from Baseline to Day 3 post evaluation. Trajectory of am and pm pain scores.

Generalized Anxiety Disorder Scale (GAD-7) – A Self-administered 7 item scale that draws from DSM-V criteria for General Anxiety Disorder (GAD) to identify GAD and measure symptom severity. It is routinely used as a tool to measure longitudinal changes and track treatment progress.

Patients are asked to rate the frequency of anxiety symptoms over the last 2 weeks on a Likert Scale (0-3). In general, patients with GAD or other common anxiety disorders exhibit GAD-7 scores of 10 or greater.

Pain Catastrophizing Scale (PCS) - The assessment of thoughts and feelings of the patients will be assessed using questions that are rated 0 for not at all to 4 for all the time. The Pain Catastrophizing Scale (PCS) assesses the extent of catastrophic thinking due to low back pain according to 3 components: rumination, magnification, and helplessness. It is a 13-item scale, with a total range of 0 to 52. Higher scores are associated with higher amounts of pain catastrophizing.

Composite Pain, Enjoyment and General Activity Scale (PEG) Assessment of pain intensity and interference. We will compare scores before and after initiation of Auricular Acupressure.

Patient Global Impression of Change (PGIC) – patient reported assessment of improvement or decline of their pain

PROMIS Sleep disturbance – patient reported outcome on the quality of their sleep.

Acupressure Acceptability questions - We will ask acceptability questions. "How satisfied were you with how your pain has been treated?" using the Likert scale to measure "Very satisfied =5, Satisfied=4, Somewhat satisfied = 3, Somewhat dissatisfied= 2, Dissatisfied 1, Very Dissatisfied 0. Would you consider using auricular acupressure in the future for pain or if recommended by your nurse or physician? a. No, would not use again (Score of 0) b. Maybe (Score of 1), c. Yes, I would consider using in the future (Score of 2) 3. Is there anything else you would like to tell us that may be helpful for us to know regarding ear acupressure? (Each answer will be collected and assessed for future studies).

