^c Participants will receive reminders to complete the study questionnaires twice a day

^d Only participants who agree to participate in the optional recording/photography at the time of informed consent will have their acupressure placement session recorded

Analytical Plan

Sample Size:

This is a feasibility study with no control group. Target enrollment is 20 participants. Data from this study will be used to generate parameter estimates to calculate power for future studies.

Analysis Plan:

Since this is a feasibility study, results will be analyzed initially using descriptive statistics of main outcome measures. Any group comparisons will be done using chi square tests for proportions, and t-tests or ANOVA procedures for continuous variables. Other inferential statistical analysis will be conducted as appropriate.

Human Subjects Protection

Subject Recruitment Methods

Any patient who is on the chronic pain/addiction consult service be approached by either Primary Investigator or study staff regarding participation. Only eligible patients willing to complete all survey's pre and post procedures and provide written consent will participate. If eligible, the participant will be consented by study personnel in their private hospital room. If a family member or visitor is present, the study team member will ask the participant permission to discuss the study at that time or if they would prefer to discuss another time. The study team will ensure that the participant understands the voluntary nature of participating in the research study and that study participation study will not affect the care that they will receive.

The study personnel will maintain a record of eligible study participants separate from the study files. This list will include name, MRN, and hospital room number and

enrollment status. The list will be kept in a secure file on a secure computer, separate from the study files and only accessible to study staff. The file of eligible participants will be destroyed at the end of recruitment.

Informed Consent

Signed informed consent will be obtained from each subject prior to any study procedures being performed. Any study related procedures will adhere to ICH-GCP standards.

Confidentiality and Privacy

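### One of the two scored acupressure acceptability items asks about pain treatment in general, so it cannot separate satisfaction with ear acupressure from satisfaction with concurrent pain care

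*Combined protocol and SAP*

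**What the plan says.** The secondary outcomes in the protocol's Outcome Measures section include a set headed Acupressure Acceptability questions. It has three parts.

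- **Item 1** asks "How satisfied were you with how your pain has been treated" and is scored "Very satisfied =5, Satisfied=4, Somewhat satisfied = 3, Somewhat dissatisfied= 2, Dissatisfied 1, Very Dissatisfied 0".
- **Item 2** asks "Would you consider using auricular acupressure in the future for pain or if recommended by your nurse or physician", with answers scored 0 (no), 1 (maybe) or 2 (yes).
- **Item 3** is open text: "Is there anything else you would like to tell us that may be helpful for us to know regarding ear acupressure".

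The Objectives describe the intervention as "the addition of auricular acupressure to the typical pharmacological regimen given to patients on the chronic pain/addiction service". The inclusion criteria open with "Patient admitted to the hospital with a chronic pain/addiction medicine service consult". The Sample Size paragraph of the Analytical Plan states: "This is a feasibility study with no control group. Target enrollment is 20 participants". The End of Study Assessment section and the schedule of activities both place the acceptability questionnaire on Day 3 only. The Analysis Plan foresees descriptive statistics first, with general-purpose tests for any comparisons. It defines no acceptability total, no leading item and no threshold.

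**The concern.** Item 1 sits under an acupressure label, but its wording covers everything done for the participant's pain. In this population that includes the drug regimen and the advice of the consult service as well as the ear pads. A participant who disliked the drug management but valued the acupressure could score low, and one with the opposite experience could score high. Reported as acupressure acceptability, either score would mislead.

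Acceptability is a result that a small single-arm study can describe validly without a comparator, provided the question names the intervention. A satisfaction rating specific to acupressure would inform the design of a later trial. As written, the plan does not obtain one.

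**Working it through.** The plan gives no figure to reproduce here, so the check is a reading of the items against the design.

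**Step 1. What each item refers to.**

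| Item | Names ear acupressure? | Scored? | Range | What it asks about |
|---|---|---|---|---|
| 1 | No | Yes | 0 to 5 | Satisfaction with pain treatment |
| 2 | Yes | Yes | 0 to 2 | Intention to use in future |
| 3 | Yes | No | Free text | Comments |

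Two of the three items name the intervention; the one satisfaction rating does not. Among scored items, 1 of 2 is non-specific, and 0 of 2 asks about satisfaction with acupressure.

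**Step 2. What else item 1 can pick up.** By the inclusion criteria every participant has the consult, and by the Objectives acupressure is added to the service's typical drug regimen. Pain treatment other than acupressure is therefore present by design for all of the planned 20 participants.

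**Step 3. Whether the design could separate the sources.**

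- *Between participants:* with no control group, nobody receives the usual care without the acupressure, so there is no contrast.
- *Within participants:* the questionnaire is given once, on Day 3, so no change in satisfaction can be formed. Even a baseline rating would help only in part, because the rest of the inpatient pain care continues over the same days.
- *By analysis:* nothing in the Analysis Plan distinguishes item 1 from the rest of the acceptability set or adjusts it for concurrent care.

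A score on item 1 is thus a mixture of satisfaction with acupressure and satisfaction with other pain care. None of the data planned for collection identifies the two parts.

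**Step 4. How far the problem spreads.** The plan does not combine the items. If they are reported separately, the wording of item 1 has no effect on items 2 and 3. Those remain usable as measures of intention to use acupressure and of participants' comments on it.

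**The case against.** There are four arguments on the other side.

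1. **The set already contains acupressure-specific questions.** Willingness to use the treatment again is a direct measure of acceptability, and the free-text answers are to be assessed for future studies. This stands, and it confines the problem to item 1. It does not supply a satisfaction rating for acupressure, because item 2 asks about intention.

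2. **General satisfaction is a reasonable question for an adjuvant added to usual care.** This also stands. The fault lies in filing the answer under acupressure acceptability, so the question can be kept under its own label.

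3. **The questionnaire itself is not visible.** Appendix I is listed by title only, so an introduction that narrows how participants read item 1 cannot be excluded. That is a real limit. Even so, the Outcome Measures section gives the item's wording and scoring as the protocol's own definition, and that wording is not specific.

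4. **Little depends on this item.** Acceptability is one of several secondary outcomes, with no threshold or progression rule attached. Feasibility is also informed by interventionist time, the placement survey, fidelity recordings and participants' notes of fallen pads. This stands and limits the consequences.

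A reader might also infer that item 1 is the main acceptability item, or that the acceptability result will mostly reflect opioid and consult care. The documents support neither. They rank none of the items, and they give nothing from which the share of item 1 due to each source could be calculated. Nor should a weight be read into the scales. Item 1 would supply 5 of 5 + 2 = 7 possible points (71%) only if the two scored items were added, and the plan defines no such sum.

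**Conclusion.** The point holds for item 1 alone. That item cannot separate satisfaction with ear acupressure from satisfaction with concurrent pain care, and no analysis of the planned data can repair this afterwards.

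Its size is one of two scored items, in a secondary outcome of a 20-participant feasibility study. The direction and amount of any distortion cannot be derived from the documents, so no claim is made that acceptability will come out too high or too low. The acceptability outcome as a whole is not invalid.

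The conclusion assumes that the questionnaire in Appendix I uses the wording given in the Outcome Measures section, and that participants take the question at face value. The change is worth making because it is nearly free and gives the study a satisfaction rating of its own intervention.

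**What to change.** In the Acupressure Acceptability paragraph, and in Appendix I if its text matches, reword item 1 to ask how satisfied the participant was with the ear acupressure received. Keep the same six response levels, 0 to 5. If satisfaction with overall pain treatment is also wanted, keep the current question as a separately labelled item and report it outside the acceptability outcome. If Appendix I differs from the protocol text, reconcile the two.

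If data have already been collected, report item 1 as general pain-care satisfaction and base acupressure acceptability on items 2 and 3. State that no satisfaction rating specific to acupressure was obtained.

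The cost is a minor amendment and at most one extra question on Day 3. Sample size, visit schedule and other outcomes are unaffected.

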Each study participant will be asked to sign a separate consent giving permission for the intervention to be recorded and used for educational and research purposes. The recordings will be done to limit exposure of the study participant’s face.

The interventionist's time will be measured in minutes from time the interventionist enters room to place acupressure pads to when the interventionist exits room. Qualitative questions will be used to assess overall feasibility.

- The study team will perform the pain score assessment with participants (on 0-10 NRS scale) two (2) times a day for 3 days. If the study team is unable to perform the pain scores assessment in person, we will use the pain score that has been assessed by the clinical team as part of their regular care and documented in the participant's medical record.

Study participants will be reminded to complete their daily study activities.

- A member of the study team will remind the participant to complete their assessment(s) or the study nurse can place an order in Wake One to prompt the care team to remind the participant.
- A sign will be placed in the participant's room reminding them to complete their study activities.

Monitoring opioid usage: data abstraction will be done and verified in Wake One if the participant remains inpatient for the 3 days.

End of Study Assessment:

Within 24 hours of the completion of the assessments and the removal of the acupressure beads, a member of the study team will assess patients'

- Pain scores
- Opioid medication frequency and dosage
- Verify completion of Day 3 study questionnaires: Pain Catastrophizing Scale (PCS); Generalized Anxiety Disorder Scale (GAD-7); Pain, Enjoyment, General Activities Scale (PEG); Patient Global Impression of Change Scale (PGIC); PROMIS sleep disturbance scale

Participant will also be asked to complete "Willingness or desire to decrease opioid dependence and usage" and Acupressure Acceptability questionnaires on Day 3

Outcome Measures:

Since this is a feasibility study, results will be analyzed initially using descriptive statistics of main outcome measures.

To evaluate the efficacy of the auricular acupressure the following outcomes will be assessed:

Primary Outcomes:

Patient reported pain scores – change in patient reported pain scores (derived from the NRS and PEG scale) from baseline and Day 1-Day 3.

Secondary Outcomes to be measured:

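### The only scored acceptability item that names acupressure puts two conditions into one answer and is scheduled only at Day 3/end of study, so a Yes is hard to interpret and may overstate participants' own willingness to reuse it

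*Combined protocol and SAP*

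**What the plan says.** Under Outcome Measures, the Acupressure Acceptability entry contains three questions.

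- The first, "How satisfied were you with how your pain has been treated", is scored 0 to 5. It concerns pain treatment as a whole and does not mention acupressure.
- The second is "Would you consider using auricular acupressure in the future for pain or if recommended by your nurse or physician". Its lower options read "a. No, would not use again (Score of 0) b. Maybe (Score of 1", and Yes scores 2. The Yes option speaks of considering future use and does not repeat either condition.
- The third, "Is there anything else you would like to tell us that may be helpful for us to know regarding ear acupressure", is open text with no score.

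End of Study Assessment places the "Acupressure Acceptability questionnaires on Day 3", and the study activity table marks that questionnaire only in the Day 3/end of study column. The Analytical Plan calls for descriptive statistics of the main outcome measures. It gives no acceptability threshold, no denominator and no rule for a participant without a Day 3 form.

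**The concern.** The second question joins two conditions with an or: the participant would use acupressure for pain, or would use it if a nurse or physician advised it. Read literally, someone who saw little benefit but would follow advice can answer Yes and score 2, the same as someone who wants it again. No other scored acceptability item separates the two, because the satisfaction item covers all pain treatment and participants also receive their usual drug regimen.

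The second part is who gets asked. The protocol foresees early departure: it makes inpatient opioid abstraction conditional on staying the 3 days, and it lists risk of leaving against medical advice as a possible exclusion. Yet it makes no provision for collecting acceptability from people who withdraw or leave before Day 3. If they hold less favourable views, a percentage among completers would look better than the truth.

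The study is described as assessing the feasibility of the intervention, and acceptability is a listed outcome. A later trial team would want to know whether patients would choose acupressure again. This item as worded does not tell them.

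**Working it through.** The plan has no calculated acceptability figure to reproduce. The sample size of 20 comes without a dropout rate, an acceptability target or a precision statement. The check therefore bounds what the item could report.

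**Inputs from the documents (Analytical Plan).** "Target enrollment is 20 participants" and "This is a feasibility study with no control group". Item wording and timing are as set out above.

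**Assumed, because the documents give nothing.** All 20 have pads placed. The number of missing Day 3 forms, m, is 0, 2, 4 or 6. The Yes rate among responders is near 75%. The share willing to reuse for pain on their own account is A = 60%, and the share willing if advised is B = 70%.

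**Step 1: wording.** The Yes rate depends on how respondents read the or.

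- Read as either condition: from max(A, B) = 70% to min(100%, A + B) = 100%.
- Answered Yes only when both apply: from max(0, A + B − 100%) = 60 + 70 − 100 = 30% to min(A, B) = 60%.
- If everyone who would reuse unprompted would also do so when advised: 70% under the first reading and 60% under the second.

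Against the assumed own-use rate of 60%, the first reading is 10 to 40 points too high and the second is 0 to 30 points too low. In the nested case the item is 0 to 10 points too high. A respondent with a split view may also choose Maybe, which moves the figure again. The recorded 0, 1 or 2 does not show which reading was used.

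**Step 2: missing forms.** With y Yes answers among 20 − m responders, the reported figure is y/(20 − m). The value for all 20 lies between y/20 (no missing participant would say Yes) and (y + m)/20 (all would).

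| Missing m | Reported | All-20 range | Largest overstatement | Largest understatement |
|---|---|---|---|---|
| 0 | 15/20 = 75.0% | 75.0% | 0 | 0 |
| 2 | 14/18 = 77.8% | 70.0% to 80.0% | 7.8 points | 2.2 points |
| 4 | 12/16 = 75.0% | 60.0% to 80.0% | 15.0 points | 5.0 points |
| 6 | 10/14 = 71.4% | 50.0% to 80.0% | 21.4 points | 8.6 points |

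The reported figure lies inside every range, so the error can go either way. There is more room for overstatement because the assumed Yes rate is above one half. With no missing forms, the timing introduces no selection.

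**Step 3: sampling error.** For 15/20 the exact (Clopper-Pearson) 95% interval is 50.9% to 91.3%, about 40 points wide. The widest range in Step 2 is 30 points. An interval around the reported percentage would show the sampling error, but it would show neither the ambiguity in Step 1 nor the selection in Step 2.

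**The case against.** A reader might infer that the acceptability result will be overstated. The case against that is strong, and most of it stands.

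- **Answer options.** The No option refers to not using it again and the Yes option to future use, neither with the clinician condition. A dissatisfied participant could naturally choose No, and a conditional one could choose Maybe. Willingness on a clinician's advice is also arguably part of acceptability for an intervention that a nurse places. This weakens any claim about direction, but one answer still covers two different things.
- **Loss before Day 3 is limited.** Subject selection criteria require an expected stay of at least 5 days and allow exclusion of patients at risk of leaving against medical advice. Subject Recruitment Methods states "Only eligible patients willing to complete all survey's pre and post procedures and provide written consent will participate". There are reminders, and compensation is given at Day 3. Contact information is collected for follow-up, and inability to use a telephone is an exclusion, so discharge need not mean loss. These provisions make missing forms less likely, but none says that acceptability is to be asked of someone who leaves early.
- **Pad removal.** A reader might infer that participants who take their pads off early go unasked. The documents do not say so. A participant whose pads fall off stays in the study without replacement, and nothing says that removing them ends participation. The gap concerns withdrawal and departure.
- **Timing.** Asking about acceptability after treatment is not itself a bias. It matters only if forms are missing and those participants differ.
- **Consequence.** Acceptability is a secondary, descriptive outcome with no go/no-go rule, and no section ties this item to a later power calculation. The open question also lets reservations be recorded.

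Appendix I is listed but its content is not shown, so the check rests on the wording in Outcome Measures.

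**Conclusion.** The point holds as a minor one. The only scored acceptability item that names acupressure combines two conditions in one answer, and analysis cannot recover which was meant, whether or not any forms are missing. It may overstate own willingness to reuse. Separately, the item is scheduled only at Day 3/end of study, with no provision for those who withdraw or leave earlier. The completer figure would be too high if those people are missing and less favourable.

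The documents support neither a firm direction nor a size. They give no dropout rate, no reasons for loss and no response pattern. Every percentage above other than the sample size of 20 rests on assumed inputs and is only illustrative. The primary pain outcome is unaffected. The change is worth making because it is cheap and does not depend on which way any bias runs.

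**What to change.** 1. **Split the item.** End the scored question after future use for pain. If use on a nurse's or physician's recommendation is also of interest, ask it as a separate item with the same 0 to 2 options.
2. **Ask early leavers.** Schedule the acceptability items at Day 3, or at withdrawal or discharge if earlier. Where needed, use the telephone and the contact information already collected, for participants who agree.
3. **Fix the denominator.** Report the Yes proportion over all participants who had pads placed, with non-responders shown as a separate category.

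The cost is an edit to Outcome Measures and Appendix I, one line in the study activity table, one extra question and a few short calls. The resulting figure may be less favourable.
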